Schedule B will be initiated after preliminary safety data of AMG 673 in Schedule A (eg, MTD1 is estimated to be $\geq 72 \mu\text{g}$) become available and may be conducted in parallel with Schedule A per Sponsor's decision. For Schedule B, planned dose levels (dose per infusion) for the dose escalation cohorts are as follows: 72 μg , 110 μg , 160 μg , 240 μg , 360 μg , 480 μg and higher if MTD for Schedule B is not reached. The starting dose for the first cohort on Schedule B will be 72 μg administered as short-term IV infusions daily (QD) during the 14-day cycle 1. The doses administered for the subsequent cohorts will include step-up doses administered in increments of 2 days as described in [Table 4](#). The DLRT may recommend shortening the duration of steps to 1 day or to extend the duration of steps up to 5 days based on the emergent safety, PK and PD data. All subjects will be pre-treated with an 8-mg dose of IV dexamethasone 1 hour prior to the day 1 dose of AMG 673 and prior to each step-up dose of AMG 673 in cycle 1 and prior to all doses in subsequent cycles. Cycle 2 will start immediately after cycle 1 has completed and will consist of 4 AMG 673 infusions: day 1, day 4, day 8, and day 11 of a 14-day cycle at the target dose. Each cycle on Schedule B is planned for 14 days and intervals between cycles up to 2 weeks may be permitted after completion of cycle 2 upon discussion and agreement with Sponsor. Please refer to [Section 6.2.1.1.2](#) for additional information on Schedule B dose schedule, requirements and treatment-free intervals.

Estimation of MTDs

The estimate of the MTD or the estimate of each MTD if step dosing is used will use Bayesian logistic regression model (BLRM) design once a DLT is observed. DLTs experienced by subjects both during and after completing the DLT period will be considered in the BLRM design to account for any late onset toxicity. Schedule A may

result in 2 or more estimates of MTD; MTD1 without step dose, MTD2 with step dose and MTD3 with 2 step doses. Schedule B will utilize the step-up dose schedule described in [Section 6.2.1.1.2](#) to estimate MTD. A final estimate of the MTD and RP2D will be evaluated and confirmed utilizing all DLT evaluable subjects from the dose escalation and the dose expansion cohorts for each schedule.

MTD1 (Schedule A)

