6.2.1.1.2 Schedule B

Schedule B will be initiated after preliminary safety data of AMG 673 in Schedule A (eg, MTD1 is estimated to be \geq 72 μ g) become available and may be conducted in parallel with Schedule A per sponsor's decision. For Schedule B, planned dose levels (dose per infusion) for the dose escalation cohorts are as follows: 72 μ g, 110 μ g, 160 μ g, 240 μ g, 360 μ g, 480 μ g and higher if MTD is not reached. The drug will be administered as short term IV infusions (approximately 30 minutes to 3 hours). The starting dose for the first

cohort on Schedule B will be 72 µg administered as short-term IV infusions daily (QD) during the 14-day cycle 1. No significant AMG 673 accumulation following QD dosing is predicted based on the preliminary PK analysis of Schedule A dosing. The doses administered for the cohorts following cohort 1 will include step-up doses administered in 2 day increments after the previous step-up dose (eg, cohort 2 will start with 72 µg for 2 days followed by 110 µg administered from day 3 to day 14; cohort 3 will start with 72 µg for 2 days followed by 110 µg from day 3 to day 4, followed by 160 µg from day 5 to day 14, etc). See [Table 3](#) below for more details.

Table 3. Schedule B - Cycle 1 Dosing

	D1 ^c	D2 ^c	D3	D4	D5	D6	D7	D8	D9	D10	D11	D12	D13	D14
Cohort 1	72 ^{ab}	72	72	72	72	72	72	72	72	72	72	72	72	72 ^b
Cohort 2	72 ^{ab}	72	110 ^{ab}	110	110	110	110	110	110	110	110	110	110	110 ^b
Cohort 3	72 ^{ab}	72	110 ^a	110	160 ^{ab}	160	160	160	160	160	160	160	160	160 ^b
Cohort 4	72 ^{ab}	72	110 ^a	110	160 ^a	160	240 ^{ab}	240	240	240	240	240	240	240 ^b
Cohort 5	72 ^{ab}	72	110 ^a	110	160 ^a	160	240 ^a	240	360 ^{ab}	360	360	360	360	360 ^b
Cohort 6	72 ^{ab}	72	110 ^a	110	160 ^a	160	240 ^a	240	360 ^a	360	480 ^{ab}	480	480	480 ^b

D = dose; Unit of dosage = µg

^a Dexamethasone 8 mg IV will be administered 1 hour prior to dose.

^b Additional PK samples will be taken at these time points as described in [Table 12-Table 14](#).

- [Table 13](#) PK sampling will be used only at the first dose of the target dose (highest dose planned) to be tested in Cycle 1 for each subject
- All subjects will undergo day 1 PK sampling as described in [Table 12](#).

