- PK sampling will occur on day 14-19 of Cycle 1 per [Table 12](#) if the subject will not receive cycle 2 immediately following cycle 1. If subject proceeds to Cycle 2, day 14 (post-dose) through day 19 samples will not be collected and Cycle 2 day 1 (eg day 15 after 1st dose) should be collected per [Table 14](#).

^c Upon recommendation of DLRT and Sponsor agreement, a lower starting dose may be used (eg, 36 µg) for up to the first 2 doses

The DLRT may recommend shortening the duration of steps to 1 day or to extend the duration of steps up to 5 days based on the emergent safety, PK and PD data. If the duration of step-up doses is extended, the duration of a cycle can be extended from 14 days to 28 days. All subjects will be pre-treated with an 8-mg dose of IV dexamethasone 1 hour prior to AMG 673 dose on day 1 and prior to each step-up dose of AMG 673.

Cycle 2 will consist of 4 AMG 673 infusions: day 1, day 4, day 8, and day 11 of a 14-day cycle at the target dose (maximum planned dose received from cycle 1) (see [Table 4](#) below). Cycle 1 schedule may be repeated 1 time before cycle 2 schedule is initiated upon agreement between the Investigator and Sponsor if the patient will likely

Approved

gain additional benefit per Investigator's assessment. If cycle 1 is not repeated, cycle 2 should begin immediately after cycle 1 with no dose free interval.

Table 4. Schedule B – Cycle 2 and Higher Dosing

	Day of Dose (14-Day Cycle)													
	1	2	3	4	5	6	7	8	9	10	11	12	13	14
Cohort 1	72 ^a			72				72			72			
Cohort 2	110 ^a			110				110			110			
Cohort 3	160 ^a			160				160			160			
Cohort 4	240 ^a			240				240			240			
Cohort 5	360 ^a			360				360			360			
Cohort 6	480 ^a			480				480			480			

Unit of dosage = µg

^a Dexamethasone 8 mg IV will be administered 1 hour prior to dose.

Upon recommendation from DLRT, the number of AMG 673 infusions in cycle 2 and higher may be adjusted based on emergent PK, safety, and PD data (eg, weekly [day 1 and day 8 of each cycle]). Subjects will be hospitalized for the whole duration of cycle 1 (ie, a minimum of 15 days), and for at least 48 hours after each AMG 673 administration in cycle 2 and higher. In the absence of any DLTs or SAEs, shorter hospitalization may be considered upon PI recommendation and Medical Monitor agreement after Cycle 2.

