DISEASE and BIOMARKER ASSESSMENTS																																											
Bone marrow assessments	X																																								X ^k		X

Footnotes defined on next page of the table

Approved

EOS = End of Study; EOT = End of Treatment; SCR = Screening

- ^a Assessments should be taken at the time specified (in hours) from the start of infusion on that day. If a time is not specified, all assessments and collections should be pre-dose.
- ^b The following assessments should be performed relative to the day 14 dose. Cycle 2 should begin immediately after Cycle 1 with no treatment free interval (see [Section 6.2.1.1.2](#)). The samples in dark gray are only collected if the subject will not initiate cycle 2 immediately after cycle 1. If cycle 2 is initiated immediately after cycle 1, then collect per [Table 14](#) (refer to footnote J).
- ^c Clinical evaluations will include physical exam, ECOG, and weight. Screening only: demographics, medical history, and height will also be obtained. Pre-dose clinical evaluation may occur up to 3 days prior to dose.
- ^d Vital signs / pulse oximetry must be collected as described above but may be collected at site more frequently per institutional policy or by recommendation of PI. Additional assessments do not need to be reported to EDC unless related to an adverse event but must be kept in source. Subjects will also be assessed prior to discharge from hospital in order to detect possible signs and symptoms of infusion reactions.
- ^e ECGs are required per [section 7.3.8](#). ECG's: At screening 2 triplicates (total of 6 ECGs) should be done, at predose C1D1: 1 triplicate (total of 3 ECGs), post 1hr -end of infusion, 24 hours post dose and at EOS. Schedule for ECGs during cycle 1 also applies in case of intra-subject dose escalation, regardless of actual study cycle.
- ^f Serum pregnancy test will be performed for all females unless surgically sterile or > 2 years postmenopausal
- ^g Refer to [Table 3](#) for planned dosing regimen

ⁱ This sample is optional. See Laboratory Manual for details on collection requirements.

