^j Cycle 1, PK samples must always be collected on day 1. In addition, enhanced PK sampling, as described in [Table 13](#), is required at the time of step-up to the maximum planned dose. This is outlined [Table 3](#). If subject is not planned to immediately initiate cycle 2 (eg, due to DLTs), day 14-19 PK samples should be collected. If subject proceeds to Cycle 2, day 14 (post dose)-19 PK samples are not collected and sampling should occur as described in [Table 14](#).

^k During the same procedure, bone marrow samples will be collected for both response and biomarker assessments. This sample is to be collected after the last dose in Cycle 1 (ie, day 14).

Approved

Table 13. Schedule of Assessments: Schedule B (Cycle 1 Step-Up Dose Visit)

Step-Up Dose Day ^a	Treatment Period ^a											
	1											2
	Pre-dose	0	1	2	3	4	6	8	12	16	20	Pre
GENERAL AND SAFETY ASSESSMENTS												
Dexamethasone administration 1 hr before prior	X											
Clinical Evaluation ^c	X											X
Vital signs, pulse oximetry ^d	X	X	X	X	X	X	X	X	X	X	X	X
ECG triplicate measurement ^e	X	X ^f										X
LABORATORY ASSESSMENTS												
Coagulation	X						X					X
Hematology, Chemistry	X						X					X
Urinalysis	X											
INVESTIGATIONAL PRODUCT DOSING												
AMG 673 short term IV Infusion		X										X
PK ASSESSMENTS												
AMG 673 PK Collection ^f	X	X				X	X					X

EOS = End of Study; EOT = End of Treatment; SCR = Screening

^a Step-up doses are defined in Table 3. Day 1 in this schedule is each day where the planned dose is higher than the previous day.

^b Hours are calculated from the start of initial infusion of the higher dose (step-up)

^c Clinical evaluations will include physical exam, ECOG, and weight. Screening only: demographics, medical history, and height will also be obtained. Pre-dose clinical evaluation may occur up to 3 days prior to dose.

^d Vital signs / pulse oximetry must be collected as described above but may be collected at site more frequently per institutional policy or by recommendation of PI. Additional assessments do not need to be reported to EDC unless related to an adverse event, but must be kept in source.

^e ECGs are required per section 7.3.8. Triplicate ECGs are required at the times described above.

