7.2 General Study Procedures

A signed and dated IRB/IEC approved ICF must be obtained prior to performing any study-specific procedures including discontinuing standard therapy for observing a study washout period.

During the study, every effort should be made to perform the study procedures as indicated on the Schedules of Assessments ([Section 7.1](#)). In case of a new dose step (ie, subject receives a dose in a later cycle that they have never received before), cycle 1 assessments apply.

Subjects will be seen in the clinic for study evaluations. When electrocardiograms (ECGs), vital signs, blood sample collections, biomarker sample collections, and aspirate/biopsy sample collections occur on the same visit, ECGs and vital signs should be performed before samples (blood, biopsy/aspirate) are collected. Blood samples must not be taken/drawn from the catheter port used for AMG 673 infusion. If a permanent central line with more than 1 lumen is used, blood draws can be done via the lumen that is not used for drug administration (see also [section 7.3.12](#)). The time of blood sample collection must be recorded with the exact time of collection (do not use the time that the samples were frozen or any other time point). For blood samples scheduled on the day of an infusion, the blood sample should be taken prior to infusion start unless indicated otherwise in the schedule of assessments.

The study specific manuals provide additional details regarding the requirements for these procedures.

Acceptable deviation windows are as follows (any greater deviations require the sponsor approval):

- Dose time \pm 10 minute window.
- ECGs, biomarker blood draws (cycles 1 – 3), vital signs (incl. pulse oximetry):
 - \pm 15 minute window if collected within the first 24 hours (excluding the 24 hour sample) after the start of an infusion (or dose step, if applicable).
 - \pm 2 hour window if collected between 24 hours and 3 days after the start of an infusion.
 - Assessments after day 3 post infusion start should be performed on the indicated study day, but not at a certain hour of the day.
 - \pm 1 day window if collected 1 week after infusion start or later, or at the EOI.
- Bone marrow assessments post treatment start: \pm 3 days

- PK blood draws in cycles 1 - 3:
 - within 2 hours prior to infusion start
 - \pm 15 minute window for samples taken within the first 24 hours after start of each infusion and within 24 hours after EOI for each infusion.

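### In Schedule B cycle 1, a 3-day allowance lets the examination scheduled before a step-up be done before both infusions of the preceding 2-day step

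*Protocol*

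**What the plan says.** Protocol Section 3.1 describes the Schedule B cohorts after the first as having "step-up doses administered in increments of 2 days". Section 6.2.1.1.2 and Table 3 set this out day by day. Cohort 3, for example, receives 110 µg "from day 3 to day 4, followed by 160" µg. On step length the same section adds: "The DLRT may recommend shortening the duration of steps to 1 day or to extend the duration of steps up to 5 days".

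Table 13 in Section 7.1 governs step-up visits. Its footnote a reads: "Day 1 in this schedule is each day where the planned dose is higher than the previous day". The table schedules a clinical evaluation in the column headed Pre-dose on the step-up day, and another in the column headed Pre on the following day.

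Footnote c of Tables 12 and 13 defines the evaluation as physical examination, ECOG and weight, and adds: "Pre-dose clinical evaluation may occur up to 3 days prior to dose". Nothing confines this to the first dose.

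Table 12 also has a general timing rule in footnote a: "Assessments should be taken at the time specified (in hours) from the start of infusion on that day" and "If a time is not specified, all assessments and collections should be pre-dose". Section 7.2 lists tolerance windows for dosing, ECGs, vital signs, biomarker draws, bone marrow and PK samples. It lists none for the clinical evaluation.

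**The concern.** An examination scheduled before a dose increase should show how the subject tolerated the dose just given. An allowance of 3 days does not guarantee that when a step lasts 2.

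The same sentence appears in the Schedule A tables, where it does little harm. On nominal days the evaluation for D5 can be no earlier than D2, which is after the D1 infusion. With daily dosing and short steps the sentence works differently. For laboratory tests, Section 7.2.2 gives only 24 hours, and only at treatment start.

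At stake is one layer of safety assessment in a first-in-human step-up. Section 7.3.5.1 includes the neurological system in the physical examination. Table 1 lists neurotoxicity as a potential risk and notes that, for blinatumomab in ALL, most such events came in the first cycle. Vital signs, ECG and laboratory tests do not replace a neurological examination.

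**Working it through.** The plan states no figure on this point, so the check is date arithmetic on Table 3.

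**Inputs.** Daily infusions D1 to D14 and 2-day steps (Section 6.2.1.1.2, Table 3). Step-ups on D3, D5, D7, D9 and D11, depending on cohort. Allowance of 3 days (footnote c). There is no day 0, so 3 days before D3 is D-1.

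**Earliest permitted evaluation** = step-up day minus 3 days.

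| Step-up | Earliest evaluation | Infusions of preceding step | Dose ratio |
|---|---|---|---|
| D3 | D-1 | D1, D2 | 110/72 = 1.53 |
| D5 | D2 | D3, D4 | 160/110 = 1.45 |
| D7 | D4 | D5, D6 | 240/160 = 1.50 |
| D9 | D6 | D7, D8 | 360/240 = 1.50 |
| D11 | D8 | D9, D10 | 480/360 = 1.33 |

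In every row the earliest evaluation precedes both infusions. Cohorts 2 to 6 have 1, 2, 3, 4 and 5 step-ups, and it holds at all 1 + 2 + 3 + 4 + 5 = 15 of them.

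**Other step lengths.** For a step of L days before step-up s, the evaluation must be done before the infusion on day s−L, and no earlier than day s−3. Both are possible only if L ≤ 3. So it can happen with steps of 1, 2 or 3 days (at 3 days, only if done before that day's infusion), and not with 4 or 5.

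**When no examination at all falls within the preceding step.** Moving the step-up evaluation is not enough. Table 13 has another evaluation before the infusion on step day 2, which is day s−1. Done on that day, it follows the infusion on s−2, so the last examination covers one of the two infusions. A full gap needs that evaluation moved to before the infusion on s−2 as well.

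Suppose footnote c covers step day 2. A full gap at s puts the evaluation for s between day s−3 and the infusion on s−2. That examination falls after the infusion on s−4 and before the one on s−2, so there cannot also be a full gap at step-up s−2. The gap can therefore occur at most at every other step-up. For k step-ups the ceiling is k/2 rounded up: 1, 1, 2, 2 and 3 for k = 1 to 5. In cohort 6 the days would be D3, D7 and D11.

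**Example, cohort 3.** Suppose D3's evaluation is done on D1, D4's on D2 and D5's on D3, each before that day's infusion, and D6's on D6. No examination then falls between the first 110 µg infusion (D3) and the first 160 µg infusion (D5). Each shift is 2 days, and no examination is counted twice.

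**Limit of the source.** For D3, the second day of the preceding step is D2, which Table 12 governs. The columns of its clinical-evaluation marks cannot be read reliably in the extracted text, so the D3 case is less certain than the others.

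**The case against.** What matters clinically is when the subject was last examined, not which visit the examination is booked against. Footnote c speaks of the pre-dose evaluation, and Table 13 heads the step-up column Pre-dose but the next day's column Pre. It is plausible, though not certain, that the allowance reaches only the first column. Step day 2 is then fixed to its day and the full gap at D5 to D11 disappears. This objection stands as far as the full gap and the counts are concerned, which is why both are conditional. It does not rescue the step-up evaluation itself, which is in the Pre-dose column on either reading. Footnote a of Table 12 does not rescue it either, because footnote c is the specific exception.

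The example is also an unlikely pattern for inpatients, and Section 7.2 asks sites to make every effort to follow the schedule. That is fair: the wording permits the pattern, but nothing suggests it would be common.

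A reader might also infer that after an adverse-event interruption the D2 and D3 evaluations required by Section 6.2.1.4 could be done before the restart dose. The context does not support that. The section is about observation after restart, under medical supervision and with at least 72 hours in hospital.

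Finally, other controls remain. Vital signs, oximetry, ECG and laboratory tests are scheduled before the step-up infusion without this allowance. Section 6.6 requires intensive CRS monitoring through infusion and for at least 4 hours afterwards. Subjects stay in hospital for all of cycle 1. This limits the size of the point but leaves the physical examination exposed.

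**Conclusion.** The point holds, as a minor safety improvement. With default 2-day steps, footnote c lets the evaluation for any planned step-up be done before both infusions of the preceding step, ahead of a 1.33- to 1.53-fold increase. If the step day 2 evaluation is done on its day, one of the two infusions is still covered.

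The ceilings of 1, 1, 2, 2 and 3 per subject rest on reading footnote c to cover step day 2, on both evaluations being moved early and, for D3, on a Table 12 mark that could not be read. They are not expected frequencies.

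Two stronger readings should be resisted. A reader might infer that subjects can be escalated with no safety check between steps; the same-day measurements, CRS monitoring and inpatient observation contradict that. A reader might also infer that DLTs would be missed or the MTD biased. The documents show no such effect: adverse events are recorded continuously, and interruption rules depend on events, not on a scheduled examination.

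**What to change.** In footnote c of Tables 12 and 13, limit the 3-day allowance to the first dose of cycle 1, where no AMG 673 infusion falls between evaluation and dose. Require the evaluations before each step-up and on step day 2 to be done on that day, before infusion. This also settles whether the allowance reaches step day 2.

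The cost is a footnote change and slightly less scheduling flexibility. Subjects are already in hospital and the evaluations are already scheduled, so no visit or procedure is added. Saying in Section 6.2.1.4 that the D2 and D3 restart evaluations are done on those days is an optional clarification.

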7.2 General Study Procedures

A signed and dated IRB/IEC approved ICF must be obtained prior to performing any study-specific procedures including discontinuing standard therapy for observing a study washout period.

During the study, every effort should be made to perform the study procedures as indicated on the Schedules of Assessments ([Section 7.1](#)). In case of a new dose step (ie, subject receives a dose in a later cycle that they have never received before), cycle 1 assessments apply.

Subjects will be seen in the clinic for study evaluations. When electrocardiograms (ECGs), vital signs, blood sample collections, biomarker sample collections, and aspirate/biopsy sample collections occur on the same visit, ECGs and vital signs should be performed before samples (blood, biopsy/aspirate) are collected. Blood samples must not be taken/drawn from the catheter port used for AMG 673 infusion. If a permanent central line with more than 1 lumen is used, blood draws can be done via the lumen that is not used for drug administration (see also [section 7.3.12](#)). The time of blood sample collection must be recorded with the exact time of collection (do not use the time that the samples were frozen or any other time point). For blood samples scheduled on the day of an infusion, the blood sample should be taken prior to infusion start unless indicated otherwise in the schedule of assessments.

The study specific manuals provide additional details regarding the requirements for these procedures.

Acceptable deviation windows are as follows (any greater deviations require the sponsor approval):

- Dose time \pm 10 minute window.
- ECGs, biomarker blood draws (cycles 1 – 3), vital signs (incl. pulse oximetry):
 - \pm 15 minute window if collected within the first 24 hours (excluding the 24 hour sample) after the start of an infusion (or dose step, if applicable).
 - \pm 2 hour window if collected between 24 hours and 3 days after the start of an infusion.
 - Assessments after day 3 post infusion start should be performed on the indicated study day, but not at a certain hour of the day.
 - \pm 1 day window if collected 1 week after infusion start or later, or at the EOI.
- Bone marrow assessments post treatment start: \pm 3 days

- PK blood draws in cycles 1 - 3:
 - within 2 hours prior to infusion start
 - \pm 15 minute window for samples taken within the first 24 hours after start of each infusion and within 24 hours after EOI for each infusion.

For dosing visits on D5, D12, and / or D19, a \pm 1 day time window applies (if recommended by DLRT).

Local laboratories should be used for the following assessments:

Hematology, hematological bone marrow assessments, clinical chemistry, coagulation, urinalysis, hepatitis serology, and serum pregnancy tests.

The following collections will be shipped to a central laboratory for analysis:

Blood samples for determination of serum concentrations of AMG 673 and presence of

Refer to the laboratory manual for detailed collection, processing, and shipping procedures.

Additional procedures deemed necessary as part of standard of care or as required by local laws and regulations may be performed at the Investigator's discretion.

